PLWH can be powerful change agents for HIV prevention within communities. Our research suggests that as PLWH receive ART and restore their health, they are motivated to protect their social network members and engage in prevention advocacy (i.e., encourage friends and family to seek HIV testing and care and reduce HIV risk); however, the quality of this advocacy is hampered by challenges related to message content, style and timing of delivery, and the selection of appropriate recipients for advocacy. With effective advocacy training, mobilizing PLWH to be change agents within their networks has the potential to be a “game changer” for HIV prevention, particularly in high-prevalence settings where virtually every family is touched by HIV. In the proposed research, we will conduct a randomized controlled trial (RCT) of *Game Changers*, an 8-session peer-led group intervention that aims to empower and mobilize PLWH to be agents for HIV prevention in their social networks. By decreasing stigma among PLWH and their social network members, as well as training PLWH on key strategies to engage social network members in discussions around HIV, *Game Changers* provides PLWH with the tools to do prevention advocacy and is facilitated by peers who are from participants’ communities and living with HIV. *Game Changers* was developed through an NIMH-funded R34 in partnership with the Infectious Diseases Institute (IDI), a public-private partnership in Kampala that provides care to PLWH, that trains healthcare workers on HIV care and treatment, and conducts research to address the HIV epidemic. As part of the intervention development process, the team conducted focus groups with PLWH and social network members, and engaged with community stakeholders, including a community advisory board. Our pilot RCT with 98 PLWH and 57 social network members revealed promising preliminary intervention effects on reduced internalized stigma and increased HIV-serostatus disclosure to social network members among PLWH, as well as increased condom use and HIV testing among social network members.

The **Specific Aims** are:

1. To conduct a fully powered RCT of *Game Changers* to test intervention effects on the primary outcomes of increased HIV testing, reduced condomless sex, and decreased enacted HIV stigma among social network members of participating PLWH.

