2. To test intervention effects on the secondary outcomes of reduced internalized HIV stigma, increased HIV serostatus disclosure, and increased viral load suppression among participating PLWH, and PrEP uptake among their social network members.
3. To examine whether increased HIV prevention advocacy by PLWH mediates intervention effects on their social network members’ increased HIV testing and condom use, and whether increased HIV disclosure by PLWH mediates intervention effects on social network members’ reduced HIV stigma.
4. To conduct a cost-effectiveness analysis of the intervention.

We will recruit 210 PLWH, randomizing 105 to the intervention and 105 to a no-intervention control condition. Each PLWH will be asked to recruit social network members (up to 4, with expected average of 3.5 network members per participant) to complete assessments (736 total network members, 368/arm), and test intervention effects on social networks. All participants will complete surveys at baseline, and 6-, 12-, and 18-months post-baseline. The cost-effectiveness analysis will inform policymakers about whether *Game Changers* is a feasible intervention in which to invest.

Our approach is particularly timely in the era of biomedical interventions, which require widespread penetration of effective HIV prevention and care messaging into communities. Positioning PLWH as central to the solution for controlling (vs. causing) the HIV epidemic has the potential to reduce HIV stigma and improve prevention outcomes at the individual, household, and network levels. Consistent with theories of social diffusion, cognitive consistency, and social influence, studies show peer advocacy interventions reduce HIV risk in advocates themselves.⁶⁻¹⁰ However, with the exception of our pilot work, we are unaware of studies of the effects of prevention advocacy by PLWH with family, friends and community members. If successful, the intervention will be a significant innovation for the field, as it targets advocacy to all types of social network members rather than specific peer or risk groups, and uses social network information to strategically target advocacy.

SIGNIFICANCE

HIV Prevalence Remains High in Uganda

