The intervention showed preliminary effects consistent with hypotheses. Among alters at month 5, condomless sex with main partners in the past month decreased by 7.7% (46.2% to 38.5%) in the intervention group vs. an increase of 10.5% (57.9% to 68.4%) in the control group; this was a large effect (Cohen's $d = .76$), despite marginal statistical significance in this underpowered small pilot [OR (95% CI)= 0.3 (.1-1.2), $p=.08$]. Among the 20 alters who were HIV-negative prior to the 5-month follow-up and who were not tested for HIV between baseline and the 5-month follow-up, 5 of 15 intervention alters (33.3%) vs. 1 of 5 control alters (20.0%) reported being tested for HIV post-intervention (in between 5- and 8-month follow-ups), which represents a small-to-medium effect size (Cohen's $d = .30$). In terms of mediators, alters of intervention participants were significantly more likely to report engaging in prevention advocacy discussions (mainly on HIV testing, condom use, and ART) in their social networks ($p=.04$). Note that, because we only interviewed a small number of alters for feasibility rather than to detect effects, we did not interview all alters with whom the PLWH did prevention advocacy, and PLWH did not do prevention advocacy with all alters interviewed. Thus, we would expect effects to be stronger in the proposed study, in which we will recruit a larger number of alters.

Results for PLWH also showed effects consistent with hypotheses. Compared to controls at baseline vs. follow-up, intervention participants were more likely to report engaging in prevention advocacy [b (SE) = 0.4 (0.2), $p = .017$], especially related to HIV testing, condom use, and number of partners (all $p < .05$). Intervention participants were less likely to feel internalized [b (SE) = -0.3 (0.1), $p = .012$] and anticipated HIV stigma [b (SE) = -0.5 (0.2), $p = .011$], and to have concerns about disclosure [b (SE) = -0.3 (0.1), $p = .028$], and were ten times more likely to have disclosed to a main partner [OR (95% CI) = 10.0 (1.5-67.7), $p = .022$], compared to control participants. Moreover, intervention participants were more likely to report that all of their alters had been tested ($p < .10$), and that they disclosed to a greater proportion of alters ($p=.05$). The intervention also had effects on social network structure: intervention participants' networks became denser over time, with more and stronger connections among alters [b (SE) = 0.1 (0.3), $p = .004$].

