To recruit alters, during the baseline social network assessment (see below), we will elicit the names of 20 alters in the PLWH's social network, and ask PLWH to identify alters who know their serostatus. In our prior studies, 87% were able to list 20 alters, and 96% were able to list at least 16 alters. At the end of the interview, PLWH will be asked to select, from the list of alters who know their serostatus, up to 7 alters whom they would be willing to refer to the study; this should be feasible, as the pilot revealed that an average of 13 of the 20 alters knew the participant's HIV status. If they refer more than 4 alters, we will randomly select 4 to target for recruitment (to limit selection bias), although we aim to recruit an average of 3.5 alters per index participant, given that we do not expect to be able to recruit 4 alters from all participants. The decision to recruit 4 is based on a need to balance interviewing enough alters to be sufficiently representative of the person's network, while also being feasible to collect the data from the large sample of overall alters in a longitudinal design. We will request that the PLWH call each selected alter at the end of the interview, and to describe the study opportunity in the presence of the interviewer, who can then immediately schedule a study visit. If any of the 4 refuse to participate or cannot be reached, we will randomly select additional alters on the list of those referred from the index participant until 4 have agreed and enrolled; if only 4 were referred, we will ask the PLWH to refer additional alters, if possible. To enhance alter enrollment, we will allow for phone-based interviews and for staff to travel to meet alters outside of Kampala after the first study visit, and provide a sufficient incentive to cover transport costs; nonetheless, our request for index participants to refer up to 7 alters allows for a 50% alter enrollment rate, in order to achieve our goal of enrolling 3.5 alters per index participant. Given the large number of alters (105/cohort; 210 for two cohorts at the same time), alters will be interviewed over a 2-month period (~25-30 alters per week) at baseline and follow-up. We used similar procedures successfully in our pilot.

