Social Network (PLWH only). We will use a longitudinal personal, egocentric network approach to assess the network of ties surrounding PLWH participants, the range of alters whom participants interact with, and participants' understanding of connections among alters.¹¹³⁻¹¹⁶ This assessment is only for purposes of evaluation and not related to the simpler, paper and pencil bullseye elicitation process that is part of the intervention content (and thus not a factor in scaling up implementation). *Alter Elicitation:* Participants will list first names and last initials of 20 individuals with whom they have been in communication in the past 6 months (e.g., in person, phone, text), starting with those most important to them. Research has demonstrated that 20 alters reliably captures variability for most network characteristics.¹¹⁷ *Network Structure:* Respondents will indicate whether they think each unique pair of alters knows each other and how often they interact. Each affirmative response corresponds to a link in a network diagram between two alters. Based on this information, one can determine how interconnected the network is.^{32, 33} Using Egoweb,¹¹⁸ we will derive *density*, the proportion of ties that exist relative to the total number of possible ties; *Alter Degree Centrality*, the number of relationships a network member has (importance/ connectedness); and *Components*, groups of three or more individuals completely separated from others (connected only to the PLWH), which, when combined with the

size of the *largest component* (of groups of three or more individuals), provides information on network fragmentation.¹¹⁹ After assessing network structure, the interviewer will use Egoweb's network visualization capabilities to create a network diagram that will be used to ask open-ended questions about clusters of individuals or well-connected individuals, to understand relationships around prevention advocacy. We will ask participants to identify alters with whom they have talked the most and least about HIV, and describe the last HIV conversation they had with an alter. We used similar questions to interpret results in our prior work.⁷⁸

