Network Composition: Using PLWH's reports, we will assess alters' demographics; relationship (e.g., family, friend, partner) and closeness to ego (PLWH); interaction frequency; and usual mode of interaction (e.g., in-person, text). For each alter, we will ask the PLWH if they have disclosed his/her serostatus to the alter, and if the PLWH knows the alter's serostatus and testing status. If the participant thinks the alter is HIV-positive, we will ask whether the participant thinks the alter is in care and on ART. To assess prevention advocacy, we will ask participants if they have encouraged each alter regarding HIV protective behaviors (e.g., HIV testing, PrEP, condom use, ART use if positive). By assessing alter characteristics, we can measure the context of prevention advocacy, i.e., characteristics and network position of individuals who are prevention advocacy recipients. To assess enacted stigma among alters, participants will be asked whether they have heard each alter express stigmatizing beliefs (ever and since last assessment), as we have done previously,¹²⁰ whether they have avoided the alter because they believe he/she would mistreat them (anticipated stigma) and whether the alter has rejected them (enacted stigma). We will derive network composition indicators (% of different types of alters; e.g., men/women, disclosed to, tested).

At each follow-up, we will use Egoweb's longitudinal features developed in our prior research to update network information. Participants will be asked the network elicitation questions, and then shown a list of alters from the prior assessment, allowing them to match alters named at follow-up against those previously included. The few personal social network studies that have measured networks longitudinally suggests that networks can change substantially in a short time.^{121, 122} These methods allow us to examine whether the intervention is associated with network change, e.g., greater density, as in the pilot.

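### Enacted stigma, a primary outcome, has a rejection item with no recall window and a beliefs item whose windowed form has no baseline value; its denominator is also not stated

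*Combined protocol and SAP*

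**What the plan says.** Specific Aims, Aim 1, lists the "primary outcomes of increased HIV testing, reduced condomless sex, and decreased enacted HIV stigma among social network members of participating PLWH".

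The only description of how enacted stigma is measured is under Network Composition, in the social network assessment answered by the person living with HIV (PLWH). For beliefs, "participants will be asked whether they have heard each alter express stigmatizing beliefs (ever and since last assessment". A second item, on avoiding the alter, is labelled anticipated stigma. The third is "and whether the alter has rejected them (enacted stigma". The beliefs item has two recall forms; the rejection item has none.

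The people asked about come from the name list under Social Network (PLWH only): "Participants will list first names and last initials of 20 individuals with whom they have been in communication in the past 6 months". That list is not limited to people who know the PLWH's serostatus. Disclosure is recorded separately for each alter, and the Recruitment section reports from the pilot that "an average of 13 of the 20 alters knew" the participant's status. The alters who enrol are a different group: their eligibility criteria require that they already know it.

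Statistical Analysis, Aims 1-3, tests each outcome by the interaction of arm with timepoint, baseline against follow-up. It does not say which stigma items form the outcome, which recall form is used, or over which alters it is computed.

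**The concern.** An arm-by-time test needs the same quantity at baseline and at follow-up. Neither stigma item clearly supplies one.

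- **Rejection.** With no window, the literal reading is whether it has ever happened. An alter who rejected the PLWH years ago then counts as positive at every visit while still on the list. Those carried-forward positives appear in both arms and pull the comparison towards no difference.
- **Beliefs.** The *ever* form has the same carry-forward. The form covering the time since the last assessment avoids it at follow-up, but there is no last assessment at baseline, so the baseline value exists only as *ever*.

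A second gap compounds the first. The intervention is meant to raise disclosure: Aim 2 includes "increased HIV serostatus disclosure, and increased viral load suppression among participating PLWH", and pilot intervention participants reported that "they disclosed to a greater proportion of alters". The human-subjects section itself lists social rejection as a possible result of disclosing. If the outcome is taken over all named alters, treatment can enlarge the group able to reject the PLWH because of HIV. Some of a real reduction per informed alter would then be offset. At stake is whether one of three primary outcomes can show a benefit that exists.

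**Working it through.** The plan gives no stigma rate, expected stigma effect or stigma power figure; its alter power calculation covers condomless sex only. There is no stated figure to reproduce, and the rates below are assumptions.

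**1. Lifetime rejection item**

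Inputs (assumed): a fraction b of alters positive at baseline in both arms; new rejection during follow-up of 5% (intervention) and 10% (control); the same alters still listed.

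Lifetime proportion at follow-up = b + (1 − b) × new rate.

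With b = 20%:
- Intervention: 0.20 + 0.80 × 0.05 = 0.24
- Control: 0.20 + 0.80 × 0.10 = 0.28
- Odds ratio: (0.24/0.76) / (0.28/0.72) = 0.316/0.389 = 0.81

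The same events in a fixed window: (0.05/0.95) / (0.10/0.90) = 0.0526/0.1111 = 0.47.

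Range over b, with the same new rates:

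| b | Intervention | Control | Odds ratio |
|---|---|---|---|
| 10% | 0.10 + 0.90 × 0.05 = 0.145 | 0.10 + 0.90 × 0.10 = 0.19 | 0.72 |
| 20% | 0.24 | 0.28 | 0.81 |
| 30% | 0.30 + 0.70 × 0.05 = 0.335 | 0.30 + 0.70 × 0.10 = 0.37 | 0.86 |

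With baseline equal in the two arms, the arm-by-time odds ratio equals the follow-up odds ratio.

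**2. Beliefs item**

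Suppose baseline is *ever* and follow-up is since the last assessment. With the same rates, controls go from 20% to 10% and intervention from 20% to 5%. With equal baselines the interaction is still 0.47, so this mixture does not by itself favour an arm. But the apparent fall in controls comes from the change of window, and the baseline no longer measures the same quantity as the follow-up.

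**3. Denominator, only if all 20 named alters are analysed**

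Inputs: 13 of 20 alters know the status (pilot). Assumed: d = net extra alters disclosed to in the intervention arm compared with control; RR = true risk ratio per informed alter; no rejection among uninformed alters.

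Ratio seen over all alters = RR × (13 + d)/13. The reduction needed just to show no difference = 1 − 13/(13 + d).

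| True RR | d = 2 | d = 4 |
|---|---|---|
| 0.70 | 0.81 | 0.92 |
| 0.80 | 0.92 | 1.05 |
| 0.90 | 1.04 | 1.18 |

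The break-even reduction is 1 − 13/15 = 13% for d = 2 and 1 − 13/17 = 24% for d = 4.

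If uninformed alters carry half the informed rate, break-even falls to 1 − 16.5/17.5 = 6% and 1 − 16.5/18.5 = 11%. If the rates are equal, it is zero.

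**The case against.** Several counter-arguments have force.

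- **The questionnaire is not in the documents.** The protocol summarises the items, and the fielded rejection question may carry a window. If so, the remedy is to state it. The current text does not.
- **The list is renewed.** A reader might infer that a lifetime item can never fall. That holds for one alter followed over time, but names are elicited afresh at each follow-up from recent contacts. An alter who rejected the PLWH can drop off the list, so a network percentage can fall and the carry-forward is partial.
- **The denominator is open.** A reader might infer that stigma is counted over all named alters. The documents fix who is asked about, not who is analysed. The analysis section describes clustering only among referred alters, and enrolled alters all know the status at entry. If they form the analysis set, the disclosure mechanism largely disappears. The all-alter reading is still plausible, because the same section derives network percentages and the described alter survey has no stigma item.
- **The mechanism is conditional.** Stigmatizing beliefs can be heard from someone who does not know the status, and the rejection item as worded is not limited to HIV. Controls may also disclose over 18 months, so the documents do not support saying that the exposed pool grows in the intervention arm only. The pilot gives a p-value of .05 for disclosure to alters, but no size.
- **Rejection after new disclosure is a real effect.** It is a foreseen harm, and newly informed alters are central to Aim 3's disclosure pathway. Removing them from the primary outcome could flatter the intervention.

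The last point stands, and it is why the baseline-informed set is proposed below as supportive only. None of these points removes the need for one recall window.

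**Conclusion.** The recall-window defect stands whichever alters are analysed. As written, the rejection item is lifetime and the beliefs item has no windowed baseline, so the stigma outcome is not the same quantity at baseline and follow-up. Under the stated assumptions the lifetime item turns an odds ratio of 0.47 into 0.81 (0.72 to 0.86 for baseline positives of 10% to 30%). List turnover would leave the result somewhere between the windowed and lifetime values.

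The denominator point stands as a gap in definition, not as a demonstrated bias. A reader might infer that the design will hide or reverse a true benefit. The documents do not support that: they give neither a stigma rate nor a number of new disclosures, and the calculation runs from mild dilution to reversal according to the inputs. What can be said is that one admissible choice of denominator allows dilution or masking, and the plan does not say whether that choice is made.

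**What to change.** 1. Ask the beliefs and rejection items over the past 6 months at every visit, including baseline, and do not use *ever* in the outcome. This matches the visit interval and the window already used for sexual behavior and prevention advocacy. The cost is one time phrase in the items.
2. State in the analysis plan which items make up enacted stigma, how they are combined, the unit of analysis and the denominator: all named alters, enrolled alters, or a network percentage. The cost is a few sentences.
3. Add a supportive analysis in alters recorded at baseline as knowing the PLWH's status. That set is fixed before randomisation, because the envelope is opened after the baseline survey, and it avoids selecting on disclosure that follows treatment. Report stigma from newly disclosed alters separately and do not drop it.

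The supportive analysis has a small data-collection cost: the items must also be asked about baseline alters who are not re-named at follow-up. The prior list is already shown to the participant for matching, so this adds some questions to an existing step.

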3: Positive Living, HIV Facts and Myths, and Introduction to Social Networks	
 Share experiences with disclosure and coping with stigma since last session; provide reinforcement and problem solving of challenges Present accurate HIV information and address common HIV myths Discuss how credible advocacy for HIV prevention requires being able to model behaviors in one's own life (positive living) Set personal goals related to positive living (e.g., adherence) Introduce the concept of social networks as key to doing advocacy 	Listing Social Network Members: In preparation for the next session, participants are asked to think about whom they consider the 20 most important people to them
4. Prevention Advocacy I	
 Share experiences with disclosure and advocacy since last session; provide reinforcement and problem solve challenges Show participants how to map their own social network and identify alters to whom they have disclosed and discussed prevention, and to whom they would like to do so Define the concept of strategically positioned alters and discuss where strategically positioned alters are in participants' network maps Use network maps and strategically positioned alters to highlight how participants can play a key role in their community through advocacy Discuss how advocacy protects others, and how PLWH are credible prevention messengers; validate fears and anxiety re: advocacy Introduce strategies for effective advocacy (teaching moments, open-ended questions, rephrasing); use role plays to build skills 	Set Personal Goals for Prevention Advocacy; Practice Prevention Advocacy: Use network map to select alters to target for disclosure and advocacy, including strategically positioned alters
5-7: Prevention Advocacy II-IV	
 Share experiences with disclosure and advocacy since last session; provide reinforcement and problem solve challenges Discuss how to support alters after they have been tested for HIV Use role playing to practice and model effective advocacy 	Same as Session 4
6: Wrap Up & Review	
 Share experiences with disclosure and advocacy since last session; provide reinforcement and problem solve challenges Use role plays to practice and model challenging scenarios Share experiences with program; Affirm commitment toward goals 	N/A

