Harm from HIV disclosure or advocacy: There is a risk that participation in the intervention sessions could result in the participant disclosing their HIV serostatus to a social network member who has a negative reaction, including discrimination, violence, hostility, social rejection, and abandonment. Engagement in advocacy discussions could also result in social network members reporting illegal behaviors to the participant (e.g., same-sex sexual behavior; sex work; not notifying sex partners of HIV infection; use of illicit drugs).

4. Adequacy of Protection Against Risks

Protection Against Risk

Informed Consent. During the consent process, potential participants will receive a detailed description of the study, including the nature of the participant's involvement in the study, the possible risks and benefits of participation, and the participant's ability to withdraw from the study at any time without consequence. The participant will have the opportunity to ask questions about the study, after which informed consent will be obtained. Each participant will be given a copy of the consent form to keep.

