Harm from HIV disclosure or advocacy. Among the goals of the intervention sessions are to improve participants' ability to make effective decisions regarding disclosure of their HIV status and engaging in HIV prevention discussions with members of their social network. These workshops will be designed to help participants recognize the full range of responses that they may encounter when disclosing their status or discussing HIV, including the potential for recipients of such information to act with hostility, violence, discrimination, or other negative responses. Hence, the workshops focus on decision-making regarding these behaviors, and improving judgment for when such behaviors will be beneficial versus harmful, rather than encouraging all participants to disclose or advocate prevention regardless of risk for harm. Further, participants are encouraged to engage in advocacy with network members who know the participant's HIV status. Participants are only eligible if they have disclosed to at least one network member; this is a criterion suggested by our IRB, in order to protect participants from others suspecting their sero-status if they engaged in advocacy without disclosure. These procedures cannot prevent all negative responses, but should minimize such risks.

If while engaging in advocacy with a network member, the network member discloses illegal behavior such as failure to notify their sex partner of their HIV infection, sex work, illicit drug use, or same-sex sexual behavior, the participant will receive training during the intervention to encourage the person to reflect on how their behavior may be related to HIV risk to themselves or others and discuss measures that could be taken to reduce this risk. The training will emphasize that the purpose of the advocacy is to protect one's family and friends and encourage protective behaviors, not to elicit or act on incriminating information.

5. Potential Benefits to Study Participants

The intervention may help clients to manage stigma and the psychological process of adjusting to HIV, to stay healthy, to make better disclosure decisions, and to engage in effective HIV prevention advocacy, with the goal of decreasing HIV rates in their social networks and communities.

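### Violence and abandonment after disclosure are named as risks, but no item or by-arm comparison measures them, and rejection is recorded only as an undefined benefit outcome

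*Combined protocol and SAP*

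**What the plan says.** Protection of Human Subjects, section 3 (Potential Risks to Participants), says that taking part in the sessions could lead a participant to disclose to someone who then has a "negative reaction, including discrimination, violence, hostility, social rejection, and abandonment". Section 4 answers with training in disclosure decisions and concedes: "These procedures cannot prevent all negative responses, but should minimize such risks".

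More disclosure is a stated goal. It is a secondary outcome under Specific Aims, and the Session 4 take-home task in Table 1 reads "Use network map to select alters to target for disclosure and advocacy".

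Under Network Composition, PLWH are asked about each alter "whether they have heard each alter express stigmatizing beliefs (ever and since last assessment"), "whether they have avoided the alter because they believe he/she would mistreat them (anticipated stigma") and "whether the alter has rejected them (enacted stigma"). The first has a time window; none is given for the other two. The same paragraph records disclosure for each alter and links alters across visits. Decreased enacted stigma among network members is a primary outcome (Specific Aims, Aim 1).

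On numbers, the recruitment section reports from the pilot that an "average of 13 of the 20 alters knew" the participant's status.

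**The concern.** The trial sets out to raise the exposure (disclosure) that carries the named risk, so the arms should be expected to differ in it. The pilot points that way: the intervention group disclosed to a larger proportion of alters (p = .05). Yet the plan describes no way to compare the arms on violence or abandonment. Rejection, the one named harm with a direct question, enters on the efficacy side, where the expected direction is a fall.

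The trial could therefore report less enacted stigma while having nothing to say on whether the disclosures it prompted went badly. Advice to policymakers would then rest on benefit and cost alone. Answers to questions that were never asked cannot be recovered at the analysis stage.

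**Working it through.** **Text check.** Each named reaction set against Assessment (Overview to Network Composition) and Statistical Analysis, Aims 1-3:

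| Named reaction | Item described | By-arm analysis as a harm |
|---|---|---|
| Violence | none | none |
| Abandonment | none | none |
| Rejection | one item per alter, no time window | none; labelled enacted stigma |
| Hostility, discrimination | indirect only (beliefs heard, avoidance) | none |

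The list of data sources in Protection of Human Subjects, section 2, has no social-harm or adverse-event form. The plan gives no power figure or expected rate for enacted stigma or for harm, so there is no stated figure to reproduce.

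**Scoring reading A: share over all listed alters.** From the plan: 20 alters listed, 13 already aware. Assumed, because the documents give no rates:
- r = proportion of aware alters who reject in the control arm
- f = relative fall in r under the intervention
- k = extra new disclosures per intervention PLWH (none in control)
- q = proportion of newly told alters who reject
- alters who have not been told do not reject

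Formulas:
- Control share = 13r/20
- Intervention share = [13r(1 − f) + kq]/20
- Break-even q = 13rf/k

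With r = 10%, f = 30%, k = 2, the control share is 1.30/20 = 6.5%. The intervention share is:
- q = 10%: (0.91 + 0.20)/20 = 5.55%
- q = 15%: (0.91 + 0.30)/20 = 6.05%
- q = 19.5%: (0.91 + 0.39)/20 = 6.5% (break-even)
- q = 25%: (0.91 + 0.50)/20 = 7.05%

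At q = 15% the outcome improves by 0.45 points, although rejections after new disclosure go from 0 to 2 × 0.15 = 0.30 per PLWH.

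The result depends heavily on the assumptions. For k = 2, break-even q runs from 13 × 0.05 × 0.20/2 = 6.5% to 13 × 0.20 × 0.50/2 = 65%. With r = 10%, k = 2 and q = 20%, a 40% fall gives (0.78 + 0.40)/20 = 5.9% (better than 6.5%), while a 20% fall gives (1.04 + 0.40)/20 = 7.2% (worse, so the problem would show).

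**Scoring reading B: enrolled alters only.** Eligibility Criteria for Alters requires that they know the PLWH's serostatus. New disclosures then contribute nothing to the outcome, and rejection that follows them is absent from it.

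**Under either reading.** The follow-up network list asks for people in communication in the past 6 months (Social Network). An alter who broke off contact may not be named, so the most complete rejections may be the least visible.

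**Precision of a PLWH-level harm item.** 105 × 0.85 = 89.25, about 89 per arm; the Statistical Power section uses 90. With zero events, the one-sided 95% upper limit is 1 − 0.05^(1/89) = 3.3%. At an assumed two-sided 5% level, 80% power exists only for contrasts such as 2% vs 13%, 5% vs 18.5% or 10% vs 26%. These figures ignore clustering by intervention group and are therefore optimistic.

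**The case against.** The strongest reply is that much of the material is already collected. Rejection and disclosure are asked alter by alter and alters are matched over time, so rejection after a new disclosure could be derived for alters still listed. PLWH in both arms are also asked about stigmatizing beliefs, avoidance, closeness, interaction frequency, social support, depression and their last conversation about HIV, so bad reactions could surface after the sessions end. This stands as a reason why the remedy is cheap. It does not supply a count of violence or abandonment, and no analysis of newly told alters is planned.

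A reader might infer several stronger things that the documents do not support:
- **That the stigma outcome is pooled over all alters and hides harm.** No scoring rule is stated, and rejection is not among the example network percentages. Under reading A the pooled share can also worsen, and when it improves it reports a true net fall.
- **That rejection is the only relevant question.** Two neighbouring items concern stigma, though neither measures violence or abandonment.
- **That this is the main risk.** It is listed third of three, unranked.
- **That facilitator notes cover one arm only.** Specific Aims, the trial overview and Human Subjects section 1 give controls no intervention, but Recruitment, Statistical Power and Aim 4 refer to an attention control. The documents leave this open.
- **That some 735 new disclosures (7 × 105) will follow.** This is a ceiling. The intervention content says participants should not feel pressured to disclose, and section 4 directs advocacy towards people who already know.

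**Conclusion.** The gap is real and should be closed. Judged on the public text, violence and abandonment are named risks with no planned measure, no harm is compared by arm, and the one direct item, on rejection, serves a primary benefit outcome whose scoring and alter set are undefined. Under one scoring, rejection by newly told alters can be offset; under the other it is excluded.

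The size cannot be stated. The rates in the working are illustrations chosen to show that the direction of a pooled share depends on unknown quantities. What is certain is the missing measurement; masking is a possibility.

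**What to change.** 1. Add two yes/no items for PLWH in both arms at baseline and months 6, 12 and 18: since the last assessment, and after disclosure or talk about HIV, (a) did anyone threaten or hurt them, and (b) did anyone end the relationship or support? Baseline needs a fixed look-back; the 6 months used elsewhere in the survey would fit.
2. Give the rejection item a since-last-assessment window. Without it, rejection cannot be placed in the interval in which disclosure took place.
3. Beside the stigma result, report by arm the number of newly disclosed alters per PLWH and how many of them rejected the PLWH. Ask the same about alters on the previous list who are no longer named; otherwise the table misses those who cut contact.
4. State how enacted stigma is scored and on which alters.

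Report the harm results as estimates with intervals, not as tests. The cost is a slightly longer interview (now 60-75 minutes for PLWH), one extra table, and counts that will be imprecise with about 89 retained PLWH per arm.
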